## **3.2** Rationale for study design, doses and control groups

A randomised crossover design has been chosen to minimise the effects of between-volunteer variability and any period effects on the overall results. The study is open-label since the primary objective is to study the bioavailability of two alternative methods of administration of crushed ticagrelor tablets compared to whole ticagrelor tablets in healthy volunteers. This study is designed in accordance with the US Food and Drug Administration (FDA) Guidance for Bioavalability and Bioequivalence (Guidance for Industry 2003, EMEA Guidance for BA 2010).

Ticagrelor will be administered as single dose, 90 mg. This is the only dose strength that is commercially available and will provide sufficient plasma exposure for the PK analyses of ticagrelor and AR-C124910XX.

Ticagrelor is rapidly absorbed following oral dosing and the half-life is 5.9 to 8.4 hours for ticagrelor and 5.9 to 20 hours for AR-C124910XX. Pharmacokinetic sampling will be performed in each dosing period and the PK sampling for up to 48 hours after the morning dose is judged to be sufficient to fulfil the objectives of the study. A 7-day washout between treatment periods minimises the risk of carry-over in this study.

## 4. SUBJECT SELECTION CRITERIA

The Investigator should keep a record, the volunteer screening log, of volunteers who entered pre-study screening.

Each volunteer should meet all of the inclusion criteria and none of the exclusion criteria for this study. Under no circumstances can there be exceptions to this rule.

## 4.1 Inclusion criteria

For inclusion in the study volunteers should fulfil the following criteria:

- 1. Provision of signed and dated, written informed consent prior to any study specific procedures
- 2. Healthy male and female volunteers aged 18 to 50 years (inclusive) with suitable veins for cannulation or repeated venepuncture
- 3. Female volunteers must have a negative pregnancy test at screening and on admission to the study centre, must not be lactating and be using (confirmed by the Investigator) a highly effective form of birth control from the time of signing the informed consent and be willing to use a highly effective form of birth control during the study until last follow up visit to the study centre. Highly effective forms of birth control are listed in Appendix E. Females of non-childbearing potential are defined as:

- Post-menopausal, defined as amenorrhea for at least 12 months following cessation of all exogenous hormonal treatments and with follicle-stimulating hormone (FSH) levels in the laboratory defined post-menopausal range
- Documentation of irreversible surgical sterilisation by hysterectomy, bilateral oophorectomy or bilateral salpingectomy but not tubal ligation
- 4. Male volunteers should be willing to use barrier contraception ie, condoms, from the first dose of the investigational product until 3 months after the last dose of the investigational product
- 5. Have a body mass index between 18 and 30 kg/m^2 (inclusive) and weigh at least 50 kg (110 pounds [lbs]) and no more than 100 kg (220 lbs).

## 4.2 Exclusion criteria

Volunteers should not enter the study if any of the following exclusion criteria is fulfilled:

- 1. History of any clinically significant disease or disorder which, in the opinion of the Investigator, may either put the volunteer at risk because of participation in the study, or influence the results or the volunteer's ability to participate in the study
- 2. History or presence of gastrointestinal, hepatic or renal disease or any other condition known to interfere with absorption, distribution, metabolism or excretion of the investigational product
- 3. Any clinically significant illness, medical/surgical procedure or trauma within 4 weeks of the first administration of the investigational product
- 4. Any clinically significant abnormalities in clinical chemistry, haematology, urinalysis, results as judged by the Investigator
- 5. Any positive result on screening for serum hepatitis B surface antigen (HBsAg), antibodies against hepatitis C virus (HCV) and human immunodeficiency virus (HIV)
- 6. Abnormal vital signs, after 10 minutes supine rest, defined as any of the following:
  - Systolic blood pressure (BP)  $<90 \text{ mmHg or} \ge 140 \text{ mmHg}$
  - Diastolic BP <50 mmHg or  $\ge$ 90 mmHg
  - Heart rate <40 or >85 beats per minute.

- 7. Any clinically important abnormalities in rhythm, conduction or morphology of resting ECG that may interfere with the interpretation of QTc interval changes. This includes volunteers with any of the following:
  - Clinically significant PR (PQ) interval prolongation
  - Intermittent second or third degree atrioventricular block
  - Incomplete, full or intermittent bundle branch block (QRS <110 ms with normal QRS and T wave morphology is acceptable if there is no evidence of left ventricular hypertrophy)
  - Abnormal T wave morphology, particularly in the protocol defined primary lead.
- 8. Prolonged QTcF >450 ms or shortened QTcF <340 ms or family history of long QT syndrome
- 9. Known or suspected history of drug abuse as judged by the Investigator
- 10. Volunteers who smoke 10 or more cigarettes per day and/or unable to abstain from smoking during the residential stay in the study centre
- 11. History of alcohol abuse or excessive intake of alcohol as judged by the Investigator
- 12. Positive screen for drugs of abuse at screening or on admission to the study centre or positive screen for alcohol at screening and on admission to the study centre prior to the administration of the investigational product
- 13. History of severe allergy/hypersensitivity or ongoing allergy/hypersensitivity, as judged by the Investigator or history of hypersensitivity to drugs with a similar chemical structure or class to ticagrelor or its metabolite AR-C124910XX
- 14. Excessive intake of caffeine-containing drinks eg, coffee, tea, caffeine-containing energy drinks and cola (more than 5 cups of coffee or equivalent per day)
- 15. Use of drugs with enzyme inducing properties (including particular attention to those that are known to inhibit or induce cytochrome P450 [CYP] 3A isoenzymes, such as St John's Wort) within 3 weeks prior to the first administration of the investigational product
- 16. Use of any prescribed or non-prescribed medication including antacids, analgesics other than paracetamol/acetaminophen during the two weeks prior to the first administration of the investigational product or longer if the medication has a long half-life. Use of systemic contraceptives as described in Appendix E, and occasional use of paracetamol/acetaminophen is allowed for minor pains and headache prior to first dose

- 17. Any intake of grapefruit, grapefruit juice, Seville oranges, Seville orange marmalade or other products containing grapefruit or Seville oranges within 7 days of the first administration of the investigational product
- 18. Plasma donation within one month of screening or any blood donation/blood loss >500 mL during the 3 months prior to screening
- 19. Has received another new chemical entity (defined as a compound which has not been approved for marketing) or has participated in any other clinical study that included drug treatment within 90 days of the first administration of the investigational product in this study. The period of exclusion begins at the time of the last visit of the prior study. Note: Volunteers consented and screened, but not administered the investigational product in this study or a previous Phase I study, are not excluded
- 20. History of haemophilia, von Willebrand's disease, lupus anticoagulant or other diseases/syndromes that can either alter or increase the propensity for bleeding
- 21. A personal history of vascular abnormalities including aneurysms; a personal history of severe haemorrhage, haematemesis, melena, haemoptysis, severe epistaxis, severe thrombocytopenia, intracranial haemorrhage; or rectal bleeding within 3 months prior to the screening visit; or history suggestive of peptic ulcer disease
- 22. Having undergone any non-minor surgical procedure during the last 3 months
- 23. History of frequent and/or significant nose bleed or clinically significant non-traumatic bleed, bruise/haematoma or any other clinically significant bleeding risk, as judged by the Investigator
- 24. Previous randomisation to treatment in the present study
- 25. Involvement of any /third party contractor or AstraZeneca employee and their close relatives regardless of their role
- 26. Judgment by the Investigator that the volunteer should not participate in the study if they have any ongoing or recent (ie, during the screening period) minor medical complaints that may interfere with the interpretation of study data or are considered unlikely to comply with study procedures, restrictions and requirements.
- 27. Volunteers who cannot communicate reliably with the Investigator

Procedures for withdrawal of incorrectly enrolled volunteers see Section 5.3.

## 5. STUDY CONDUCT

#### 5.1 **Restrictions during the study**

- 1. Fast from at least 10 hours before planned start of administration of the investigational product on Day 1. A moderate amount (not more than 200 mL) of water is allowed up to 1 hour prior to administration of the investigational product and may be resumed 2 hours after administration of the investigational product. A meal can be given 4 hours after administration of the investigational product
- 2. Eat and drink only the standardised meals and drinks provided (apart from water) during the residential period in the study centre
- 3. Abstain from consuming any of the following:
  - Alcohol from 72 hours before admission to the study centre, during the residential period and for 72 hours before the study follow-up visit
  - Energy drinks containing taurine or glucuronolactone eg, from 72 hours before admission, during the residential period and for 72 hours before the study follow-up visit
  - Caffeine-containing drinks during the residential period apart from any provided as part of a standardised meal. Excessive intake of caffeine should be avoided between discharge from the study centre and the study follow-up visit
  - Poppy seeds found in speciality bread from time of consent until after the final medical examination at the study follow-up
  - Grapefruit, grapefruit juice, Seville oranges, Seville orange marmalade or other products containing grapefruit or Seville oranges from 7 days before admission until after the final medical examination at the study follow-up
- 4. Abstain from nicotine use and smoking during the residential stay in the study centre
- 5. Abstain from drugs of abuse from time of consent until after the final medical examination at the study follow-up
- 6. Abstain from taking any medication (prescribed or over the counter products), other than paracetamol/acetaminophen from two weeks prior to the first administration of the investigational product until after the final medical examination at the study follow-up. Note: Use of systemic contraceptives as described in Appendix E, and occasional use of paracetamol/acetaminophen is allowed for minor pains and headache during the study. However, this should not obviate necessary medical treatment. If any medication is necessary during the residential period, it should be

prescribed by the Investigator and the AstraZeneca Clinical Pharmacology Alliance (CPA) Physician should be informed

- 7. Volunteers should refrain from strenuous physical activity, which is not within the volunteer's normal daily routine, from 7 days prior to admission to the study centre until after the final medical examination at the study follow-up
- 8. Abstain from blood or plasma donation until 3 months after the final medical examination at the study follow-up
- 9. Male volunteers should use a condom to prevent pregnancy and drug exposure of a partner and refrain from donating sperm or fathering a child from the time of signing the informed consent until the last follow-up visit to the study centre
- 10. Female volunteers should be using (confirmed by the Investigator) a highly effective form of birth control from the time of signing the informed consent until the last follow-up visit to the study centre. Highly effective forms of birth control are listed in Appendix E
- 11. Refrain from the use of aspirin or any other drug known to increase the propensity for bleeding from 7 days prior to Day 1 of treatment period 1 through completion of the follow-up visit (Visit 5)
- 12. Refrain from the use of non-steroidal anti-inflammatory drugs (NSAIDs; including ibuprofen) from 3 days prior to Day 1 of treatment period 1 through completion of the follow-up (Visit 5)
- 13. Refrain from the use of prescribed medication (including particular attention to those that are known to inhibit or induce cytochrome P450 [CYP] 3A isoenzymes, such as St John's Wort) from 3 weeks prior to the first administration of the investigational product through completion of the follow-up visit
- 14. Refrain from scheduling or having surgery, including dental surgery, at anytime following the screening visit (Visit 1) and through completion of the follow-up visit (Visit 5).

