#### 6.2.2 Follow-up procedures

Volunteers will return to the study centre for follow-up 5 to 10 days after the last dose of the investigational product. The follow-up visit will include the following:

- A complete physical examination
- 12-Lead paper ECG
- Vital signs (BP and pulse rate)
- Blood sampling for routine clinical chemistry and haematology measurements
- Urine sampling for routine urinalysis
- Urine pregnancy test in female volunteers only
- Concomitant medication recording
- Adverse events and SAEs will be recorded.

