#### 13.3.2 Paternal exposure

Male volunteers should refrain from fathering a child or donating sperm during the study and 3 months following the last dose.

Pregnancy of a volunteer's partner will not be considered to be an AE. However, the outcome of all pregnancies (spontaneous miscarriage, elective termination, ectopic pregnancy, normal birth, or congenital abnormality) should be monitored and documented, if possible.

The outcome of any conception occurring from the date of the first dose until 3 months after the last dose should be followed up and documented.

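### Section 5.1 item 9 releases male volunteers from the condom, sperm-donation and fathering restrictions at the follow-up visit, about 80 to 85 days before the 3-month end point set in Sections 4.1 and 13.3.2

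*Protocol*

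**What the plan says.** Section 5.1 lists what volunteers must do or avoid. Item 9 opens with "Male volunteers should use a condom to prevent pregnancy and drug exposure of a partner" and goes on to bar "donating sperm or fathering a child from the time of signing the informed consent until the last follow-up visit". Read as one sentence, the stated period applies to condom use, sperm donation and fathering alike.

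The timing of that visit is in Section 6.2.2: "Volunteers will return to the study centre for follow-up 5 to 10 days after the last dose of the investigational product". Table 1 shows it as Visit 5, the last scheduled visit.

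Two other sections deal with the same restrictions:

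- **Condom use.** Section 4.1 item 4 requires men to be willing to use condoms "from the first dose of the investigational product until 3 months after the last dose of the investigational product".
- **Fathering and sperm donation.** Section 13.3.2 states: "Male volunteers should refrain from fathering a child or donating sperm during the study and 3 months following the last dose".

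Section 13.3.2 then sets a matching reporting window: "The outcome of any conception occurring from the date of the first dose until 3 months after the last dose should be followed up".

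**The concern.** The protocol ends each of the three male restrictions at two different times. Site staff cannot apply both as written, and no text says which prevails.

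Item 9 sits in the list of volunteer restrictions, which is a natural source for what men are told. A man instructed from item 9 alone would consider himself released at Visit 5. He could then donate sperm or father a child in a period when Section 13.3.2 forbids both and requires any conception to be followed up. No later visit is scheduled at which the misunderstanding could be put right.

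What is at stake is the consistency of a participant-protection rule. The pharmacokinetic results, the sample size and the visit schedule do not depend on it.

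**Working it through.** **Inputs**

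- Follow-up visit: day 5 to day 10 after the last dose (Sections 3.1 and 6.2.2).
- End of restrictions in Section 5.1 item 9: the follow-up visit.
- End of restrictions in Section 4.1 item 4 and Section 13.3.2: 3 months after the last dose.
- Planned calendar: the study starts and ends in the third quarter of 2013 (Section 9.5).
- Longest stated half-lives: 20 hours for the metabolite and 8.4 hours for ticagrelor (Section 3.2).
- Assumption: 3 months = 90 days, with calendar months as a check.

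**End points side by side**

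| Restriction | Section 5.1 item 9 | Elsewhere |
|---|---|---|
| Condom use | Follow-up visit | 3 months after last dose (4.1 item 4) |
| Sperm donation | Follow-up visit | 3 months after last dose (13.3.2) |
| Fathering a child | Follow-up visit | 3 months after last dose (13.3.2) |
| Follow-up of conceptions | Not addressed | 3 months after last dose (13.3.2) |

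Item 9 is the outlier on every restriction it names.

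**Size of the gap**

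Gap = length of 3 months − day of the follow-up visit.

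- 90 − 10 = 80 days
- 90 − 5 = 85 days

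With calendar months counted from a last dose in July to September 2013, 3 months is 91 to 92 days:

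- 91 − 10 = 81 days
- 92 − 5 = 87 days

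Share of the 3-month period that item 9 spans:

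- 5 / 90 = 5.6%
- 10 / 90 = 11.1%

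**Does the section heading explain it?** Section 5.1 is headed as restrictions during the study, so one might expect its periods to end with the study. Item 8, directly above item 9, does not: "Abstain from blood or plasma donation until 3 months after the final medical examination at the study follow-up". The list carries post-study restrictions where they are wanted.

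**Do the women's rules explain it?** Section 5.1 item 10 ends female contraception at the last follow-up visit, and Section 4.1 item 3 gives the same end point. The women's rules agree with each other; the men's do not.

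**Drug remaining at follow-up**

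Half-lives elapsed = hours since dose / half-life.

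- Metabolite: 120 / 20 = 6 at day 5; 240 / 20 = 12 at day 10
- Ticagrelor: 120 / 8.4 ≈ 14 at day 5; 240 / 8.4 ≈ 29 at day 10

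**The case against.** The best reply is that the longer rule is already in the protocol and item 9 does not cancel it. Section 4.1 item 4 is an eligibility criterion, Section 4 allows no exceptions to eligibility, and Section 6.2.1 has the criteria reviewed with each volunteer at screening. Every man properly enrolled should therefore have been asked about condoms for 3 months, and a man who obeys all the clauses simply follows the longest. On this view the gap lies in one clause and not in the protection as a whole, and the route to harm depends on consent wording that cannot be seen here.

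A second reply is that no exposure risk is shown. The study gives three single 90 mg doses, at least 6 half-lives have passed by follow-up, and the protocol accepts the same visit as the end of contraception for the women who are dosed directly.

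Both points bear on weight, and both stand to that extent. The 80 to 85 days measure what item 9 omits, not time without any rule in the protocol, and item 9 is early only relative to the other clauses. Neither point removes the contradiction. Item 9 states its own start and end, refers to neither of the other sections, and nothing says that the longer period governs. Section 4.1 item 4 concerns willingness at entry and covers condoms only. The bar on fathering and sperm donation to 3 months appears only in Section 13.3.2, within a chapter of procedures addressed to the investigator. The sponsor chose 3 months for all three restrictions, and item 9 undercuts that choice without giving a reason.

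**Conclusion.** The concern holds as an internal inconsistency. By the protocol's own rules, Section 5.1 item 9 ends the male restrictions 80 to 85 days too early for each male volunteer, with 3 months taken as 90 days, or 81 to 87 days on the planned 2013 calendar.

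The conclusion rests on reading item 9's period as covering condom use as well as sperm donation and fathering. If it covered only the latter two, the conflict with Section 13.3.2 would remain in full.

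No pharmacological harm is claimed. The point should be corrected because it concerns an instruction meant to protect participants and their partners, and because the right end point can be read from the rest of the protocol without any outside standard.

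**What to change.** In Section 5.1 item 9, replace the end point with 3 months after the last dose of the investigational product. That closes the gap to Section 4.1 item 4, Section 13.3.2 and the conception follow-up window.

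Check that the consent information gives the same period, and have staff restate it to men no later than Visit 5.

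As a tidy-up with no safety effect, use one start point for condom use: item 9 starts at consent, while Section 4.1 item 4 starts at the first dose.

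The cost is one line of protocol text and a check of the consent form. Visits, blood samples, sample size and analysis do not change.

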# 5.2 Subject enrolment and randomisation and initiation of investigational product

The Investigator will:

- 1. Obtain signed informed consent from the potential volunteer before any study-specific procedures are performed
- 2. Assign potential volunteer a unique enrolment number, beginning with eg, 'E0001001'

- 3. Determine volunteer eligibility. See Sections 4.1 and 4.2
- 4. Assign eligible volunteer unique randomisation code (volunteer number), beginning with 1001.

If a volunteer withdraws from participation in the study, then his/her enrolment/randomisation code cannot be reused.

#### 5.2.1 Procedures for randomisation

The randomisation scheme will be generated by using the AstraZeneca global randomisation system (GRand). Utilizing a Williams design, healthy volunteers will be randomised to 1 of 6 treatment sequences in a 1:1 ratio on Day 1 of the treatment period 1 (Visit 2).

Randomisation codes will be assigned strictly sequentially as volunteers become eligible for randomisation.

## 5.3 Procedures for handling subjects incorrectly enrolled or randomised or initiated on investigational product

**Volunteers who fail to meet the inclusion/exclusion criteria** should not, under any circumstances, be enrolled or receive the investigational product. There can be no exceptions to this rule.

Where volunteers who do not meet the selection criteria are randomised in error or incorrectly started on treatment, or where volunteers subsequently fail to meet the study criteria post-initiation, a discussion should occur between the AstraZeneca CPA Physician and the Investigator regarding whether to continue or discontinue the volunteer from the investigational product.

For volunteers where there is deviation from the planned randomised sequence, they will be included and analysed according to the actual treatment sequence received.

The AstraZeneca CPA Physician is to ensure all such decisions are appropriately documented. In situations where an agreement cannot be reached, further administration of the investigational product should be stopped.

## 5.4 Blinding and procedures for unblinding the study

This is an open-label study and therefore this section is not applicable.

